Urinalysis will consist of dipstick evaluations, with a reflex microscopic evaluation if dipstick shows blood or protein is small (1+), moderate (2+) or large (3+). Spot urine protein and albumin to be done if urine > trace protein on 2 collections.

Urine pregnancy tests will be conducted for female subjects.

Laboratory tests may be repeated once at screening. Additional laboratory evaluation may be performed at the discretion of the investigator in the assessment of an adverse event, as medically warranted.

11.6 12-lead Electrocardiogram

Refer to Section 8 for 12-lead ECG assessment time points.

Single 12-Lead ECG measurements will be obtained after the subject has rested in a supine position for at least 10 minutes. External stimuli should be kept to a minimum. Video games, watching of TV, and talking will not be allowed during this time. A digital ECG machine will be utilized for the trial. If an ECG timepoint coincides with any blood samples, the ECGs will performed \pm 10 minutes from obtaining the blood sample at the same timepoint. In addition, whenever possible, subjects should not have a meal within 2 hours prior to an ECG being performed.

The ECGs will be measured using an ECG machine that automatically calculates the heart rate and measures PR, RR, QRS, QT, and QTcF (Fridericia correction formula). The same ECG machine should be used for the same subject throughout the study, if at all possible. ECGs should be conducted in adherence with a research unit SOP acceptable to the Sponsor.

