Sulpiride (Only on Non US Market)	Dogmatil, Dolmatil, Eglonyl, Espiride, Modal, Sulpor	Antipsychotic, atypical	Schizophrenia		oral, inhaled

Generic Name	Brand Names (Partial List)	Drug Class	Therapeutic Use	Risk Category	Route
Sultopride (Only on Non US Market)	Barnetil, Barnotil, Topral	Antipsychotic, atypical	Schizophrenia	A 🏼	oral, injection
Terfenadine (Removed from US Market)	Seldane	Antihistamine	Allergic rhinitis	A &	oral
Terlipressin (Only on Non US Market)	Teripress, Glypressin, Terlipin, Remestyp, Tresil, Teriss	Vasoconstrictor	Septic shock	A 🕹	injection
Terodiline (Only on Non US Market)	Micturin, Mictrol	Muscle relaxant	Bladder spasm	A 🕹	oral
Thioridazine	Mellaril, Novoridazine, Thioril	Antipsychotic	Schizophrenia	 	oral
Vandetanib	Caprelsa	Anti-cancer	Cancer (thyroid)		oral

Known Risk of TdP - Substantial evidence supports the conclusion that these drugs prolong the QT interval AND are clearly associated with a risk of TdP, even when taken as directed in official labeling.

Drugs to Avoid in Congenital Long QT - Substantial evidence supports the conclusion that these drugs pose a risk of TdP for patients with congenital long QT. Drugs on this list include those in the above three risk categories and other drugs that do not prolong the QT interval per se but they have a theoretical risk of causing arrhythmia that is based on their known stimulant actions on the heart.

Last revision: 17Dec2020 https://crediblemeds.org/

Appendix C: Algorithm for Monitoring and Management of Possible Hepatocellular DILI in Phase 2 or 3 NASH Clinical Studies

Treatment-emergentALTNormal/near normal baseline ^a :ALT \geq 5× ULNElevated baseline ^a :ALT \geq 3× baseline or \geq 300 U/L(whichever occurs first)	Treatment-emergent Total Bilirubin Normal Patients with Gilbert's syndrome: No change in baseline TBL	Liver-related Symptoms None	Action ^b Repeat ALT, AST, ALP, TBL, in 2-5 days. Follow- up for symptoms. Initiate evaluation for other etiologies of abnormal liver tests.
Normal/near normal baseline ^a : ALT ≥3× ULN Elevated baseline ^a : ALT ≥2× baseline or ≥300 U/L (whichever occurs first)	Normal Patients with Gilbert's syndrome: No change in baseline TBL	Severe fatigue, nausea, vomiting, right upper quadrant pain	Repeat ALT, AST, ALP, TBL, in 2-5 days. Follow- up for symptoms. Initiate evaluation for other etiologies of abnormal liver tests.

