5.2 Summarization of Data

Study results will be summarized by treatment group (i.e., 150 mg QD, 300 mg QD, 450 mg QD, and Placebo) in tabular format with descriptive statistics and/or in subject listings.

For placebo-corrected results, at each visit, the average placebo mean change from baseline will be subtracted from each subject's mean change from baseline.

Statistical testing will be 2-sided and performed using a significance (alpha) level of 0.05. There will be no adjustment for multiple comparisons for this exploratory study.

No imputation of missing data will be performed. No windowing of visits will be performed unless otherwise specified.

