13.2 Laboratory Tests (Hematology, Serum Chemistry, Urinalysis, and PEth 16.0/18.1 (POPEth))

Summary statistics (n, mean, standard deviation, minimum, median, and maximum) will be presented for the observed values for hematology, serum chemistry, urinalysis, and PEth 16.0/18.1 (POPEth) at each time point for the safety population, as described in Section 5.2, Summarization of Data. Summary statistics will also be presented for the change-from-baseline values to each postbaseline time point. In these displays, baseline will be defined as the last non-missing value prior to first dose of study medication. Figures will be generated appropriate to the data output.

A shift table will be presented for baseline versus each post-baseline visit for absolute neutrophil count using following grades:

- Normal: ≥ 2.5 neutrophils (10**9/L);
- Grade 1: 1.5 to <2.5 neutrophils (10**9/L);
- Grade 2: 1.0 to <1.5 neutrophils (10**9/L);
- Grade 3: 0.5 to <1.0 neutrophils (10**9/L);
- Grade 4: <0.5 neutrophils (10**9/L)

Hematology, chemistry, urinalysis, and POPEth panel results will be listed, with values falling outside the laboratory reference range flagged.

Laboratory reference ranges will be provided by the laboratory site(s) and will be included in the clinical study report.

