13.5 Electrocardiograms

Single 12-lead ECGs will be collected. For the quantitative variables RR, QRS, PR, QT, QTcF (QT interval corrected for heart rate by Fridericia's method), and heart rate, summary statistics (n, mean, standard deviation, minimum, median, and maximum) will be presented for the observed values at each time point, as described in Section 5.2, Summarization of Data. Summary statistics will also be presented for the change-from-baseline values to each postbaseline time point. In these displays, baseline will be defined as the last non-missing value prior to first dose of study medication.

The following results will be tabulated (n, %) by treatment group:

- Potential QTcF values of concern at any time post-baseline for:
 - o Increase from Baseline of >30 and <= 60 msec
 - o Increase from Baseline of > 60 msec

Post-baseline value > 500 msec

All ECG results will be displayed in subject listings for the safety population.

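### SAP 13.2 has no rule for unscheduled laboratory results and plans no by-arm count of subjects by worst post-baseline ALT, bilirubin or neutrophil value

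*SAP*

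**What the plan says.** **Laboratory tables.** SAP 13.2 plans: "Summary statistics (n, mean, standard deviation, minimum, median, and maximum) will be presented for the observed values for hematology, serum chemistry, urinalysis" and the alcohol marker PEth, "at each time point for the safety population, as described in Section 5.2, Summarization of Data". The same applies to changes from baseline. SAP 5.2 makes these displays by treatment group and adds: "No windowing of visits will be performed unless otherwise specified". The one categorical laboratory table is for neutrophils: "A shift table will be presented for baseline versus each post-baseline visit for absolute neutrophil count using following grades". All laboratory results are also listed, with out-of-range values flagged.

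**Off-schedule tests.** Protocol 7.4 (item 6) makes Appendix C applicable to raised liver tests. Its first two rows say: "Repeat ALT, AST, ALP, TBL, in 2-5 days". Its other three rows call for drug interruption with close monitoring. Protocol 11.5 also allows discretionary tests: "Additional laboratory evaluation may be performed at the discretion of the investigator in the assessment of an adverse event".

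**ECG contrast.** SAP 13.5 tabulates n (%) by arm for "Potential QTcF values of concern at any time post-baseline for" stated increases from baseline and for a stated absolute value.

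**The concern.** Safety and tolerability is a primary objective (Protocol 4.1, SAP 3). The protocol's liver rules concern individual subjects: they compare one subject's ALT with the upper limit of normal (ULN) or with that subject's own baseline, and in one row combine it with bilirubin. The planned tables describe each arm at each visit. They do not say how many subjects per arm ever reached a cut-off, whether a high ALT and a high bilirubin occurred in the same person, or whether a result drawn between visits counts. Without a rule, that last choice is made in programming and not in the plan. At stake is whether the report can show by arm the events that the protocol's own liver monitoring is set up to find.

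**Working it through.** The documents give no figure on this point to reproduce. The check is day arithmetic on the schedule, then a comparison of the planned tables with the questions they should answer.

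**1. Scheduled draws.** In Protocol 8.1, chemistry and hematology after the first dose fall on Days 28, 61 and 73, or at Early Termination. Gaps: 28 - 1 = 27 days, 61 - 28 = 33 days, 73 - 61 = 12 days.

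**2. Where an Appendix C repeat falls.** Day of trigger plus 2 to 5 days:
- Day 28 trigger: 28 + 2 = 30 to 28 + 5 = 33.
- Day 61 trigger: 61 + 2 = 63 to 61 + 5 = 66.

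Neither range contains a scheduled laboratory visit. Days 30-32 lie inside the Day 28 visit window (28 + 4 = 32), but the SAP does no windowing, so even those results have no assigned time point.

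**3. What the per-visit maximum covers.** If the triggering value is drawn at a scheduled visit, it is in that visit's by-arm maximum. Not covered are a further rise found on the repeat and a trigger that was itself drawn off schedule.

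**4. What the per-visit maximum cannot show, even for scheduled draws.**
- *Number of subjects.* An arm maximum of 400 U/L is the same whether one subject or three reached it.
- *Pairing.* The ALT maximum and the bilirubin maximum may come from different subjects. Appendix C has a row that needs both: ALT at least 3x ULN (or the elevated-baseline equivalent) with total bilirubin at least 2x ULN.
- *Baseline status.* Exclusion 32 in Protocol 7.3 admits ALT up to 5x ULN, and Appendix C uses different criteria for normal and elevated baselines. Take a rise of 4x ULN. From 1x to 5x ULN it meets the normal-baseline cut-off of 5x ULN. From 2.5x to 6.5x ULN it is 6.5/2.5 = 2.6 times baseline, below the elevated-baseline cut-off of 3 times. (This also needs 6.5x ULN to be under the alternative 300 U/L limit, so a ULN below 300/6.5 = 46 U/L; the documents give no ULN.) The maximum change is the same, but the category differs.

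**5. Neutrophils.** The shift table is per visit with no any-time row. A subject at Grade 2 on Day 28 and Grade 1 on Day 61 appears once in each visit's table, and no table counts subjects by worst grade. Unscheduled counts can arise under Protocol 11.5.

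**6. Comparison within the SAP.**

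| Measure | Cut-offs in the documents | By-arm count at any post-baseline time |
|---|---|---|
| QTcF | SAP 13.5 | Planned |
| ALT, total bilirubin | Protocol Appendix C | None |
| Neutrophils | SAP 13.2 grades | None (per visit only) |

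**The case against.** Much can be said for the plan, and several stronger readings fail.

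- **That the tables show little but means.** A reader might argue that one subject going from 40 to 400 U/L adds only 360/20 = 18 U/L to the arm mean change, and that a fall of 360/19 = 18.9 U/L in the other 19 cancels it. That is true of the mean only. Minimum and maximum are tabulated for values and changes, so at a scheduled visit this subject shows as a maximum of 400 and a maximum change of 360.
- **That unscheduled values are excluded.** The SAP does not say so. It refers to time points and visits and is silent on the rest. That they would be left out is the likely reading, not a stated rule.
- **That such events reach no by-arm table at all.** Protocol 11.7.1 makes a clinically significant abnormality an adverse event when it needs active management, such as more frequent follow-up or stopping drug. SAP 13.1 tabulates those events by arm. This route stands, but it depends on investigator judgement and carries no laboratory value, multiple of ULN or paired bilirubin.
- **That Appendix C orders the tests where neutrophil nadirs would appear.** It orders liver tests only.
- **That the 2.5 boundary for a normal neutrophil count is wrong because listings are flagged against the laboratory's range.** The documents give no lower limit for that range, the two displays serve different purposes, and placebo is graded the same way. Moving the boundary to the laboratory limit would leave Grade 1 empty if that limit were 1.5. The existing grades can stay.

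It is also fair that this is an exploratory Phase 2a trial of about 80 subjects in which every result is listed. A reviewer could find a peak by reading listings, but that does not give a pre-specified comparison by arm.

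**Conclusion.** The concern holds in limited form. SAP 13.2 has no rule for unscheduled laboratory results and no by-arm count of subjects by worst post-baseline ALT, total bilirubin or neutrophil grade, although the protocol generates unscheduled liver tests and the SAP uses the any-time method for QTcF. A peak found on a repeat would most likely be visible only in a listing or as an adverse event term. That conclusion rests on reading the SAP's silence, together with its no-windowing rule, as leaving such values out of the tables.

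The number of subjects affected cannot be estimated, because the documents give no expected rate of liver-test elevation. With 20 subjects per arm, one subject is 1/20 = 5% of an arm. The primary efficacy analysis, sample size, power and alpha are untouched. This is a cheap improvement to reporting on a primary objective. It does not show that the safety data are uninterpretable.

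**What to change.** In SAP 13.2, state that unscheduled post-baseline results are included in worst-value displays, and add n (%) by arm for the worst post-baseline value, scheduled and unscheduled:

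1. **ALT**, by the laboratory cut-offs already in Appendix C: at least 3x, 5x and 8x ULN for normal or near-normal baseline; at least 2, 3 and 5 times baseline, or the stated 300 and 500 U/L, for elevated baseline. Show the two baseline groups separately.
2. **Total bilirubin** at least 2x ULN, and the **combination with ALT within subject**, saying whether both must come from the same sample.
3. **Neutrophils**, from baseline grade to worst post-baseline grade, using the SAP's existing grades.

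State one ALT baseline for these tables. At present SAP 13.2 uses the latest pre-dose value, Protocol 11.5 averages screening and Day 1 for the exploratory analysis, and Appendix C averages two measurements at least 2 weeks apart. The symptom, direct bilirubin and INR elements of Appendix C are not needed for the table.

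The cost is one or two extra tables from data already collected, and a short addition to the SAP. The change concerns reporting only: no clinical cut-off, monitoring rule or visit is altered.

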13.3 Vital Signs

Supine vital signs will be collected. Summary statistics (n, mean, standard deviation, minimum, median, and maximum) will be presented for the observed values for systolic and diastolic blood pressures, pulse rate, respiratory rate, body temperature, and weight at each time point for the safety population, as described in Section 5.2, Summarization of Data. Summary statistics will also be presented for the change-from-baseline values to each postbaseline time point. In these displays, baseline will be defined as the last non-missing value prior to first dose of study medication. Figures will be generated appropriate to the data output.

All vital sign results will be displayed in subject listings.

13.4 InBody Scale Measurements

Summary statistics (n, mean, standard deviation, minimum, median, and maximum) will be presented for the observed values for InBody scale measurements (i.e., total body water, lean body mass, percent body fat, body fat mass, skeletal muscle mass, dry lean mass, and visceral fat) at each time point for the safety population, as described in Section 5.2, Summarization of Data. Summary statistics will also be presented for the change-from-baseline values to each postbaseline time point as well as placebo-corrected change-from-baseline values to each postbaseline time point. In these displays, baseline will be defined as the last non-missing value prior to first dose of study medication. Figures will be generated appropriate to the data output.

For body fat mass and lean body mass, a responder status (n, %) at Day 61 will be presented. A subject will be deemed a responder if their body fat mass showed a 1% or more reduction from baseline at Day 61. The same criteria will be used for the lean body mass. Additional exploratory analysis may be performed.

The responder status will also be presented for the subjects randomized only to the HbA1c between 5.7% and 9.0% subgroup.

InBody measurement results will be listed.

13.5 Electrocardiograms

Single 12-lead ECGs will be collected. For the quantitative variables RR, QRS, PR, QT, QTcF (QT interval corrected for heart rate by Fridericia's method), and heart rate, summary statistics (n, mean, standard deviation, minimum, median, and maximum) will be presented for the observed values at each time point, as described in Section 5.2, Summarization of Data. Summary statistics will also be presented for the change-from-baseline values to each postbaseline time point. In these displays, baseline will be defined as the last non-missing value prior to first dose of study medication.

The following results will be tabulated (n, %) by treatment group:

- Potential QTcF values of concern at any time post-baseline for:
 - o Increase from Baseline of >30 and <= 60 msec
 - o Increase from Baseline of > 60 msec

Post-baseline value > 500 msec

All ECG results will be displayed in subject listings for the safety population.

13.6 Lipidomic (OWL Metabolomics)

Lipidomic analyses are not described in this statistical analysis plan. A separate lipidomic analysis plan will be provided.

13.7 Metabolomic (OWL Metabolomics)

Metabolomic analyses are not described in this statistical analysis plan. A separate metabolomic analysis plan will be provided.

13.8 Proteomic (SomaScan® Assay)

Proteomic (SomaScan Assay) analyses are not described in this statistical analysis plan. A separate proteomic analysis plan will be provided.

14 PHARMACOKINETIC ANALYSES

PK analyses are not described in this statistical analysis plan. A separate PK analysis plan will be provided prior to the commencement of the study.

15 SUBJECT LISTINGS

Data that are collected and entered into the study database but that are not displayed in the summary tables that are specified in the preceding sections will be presented in subject listings. These will include (but will not be limited to) data from the following modules:

Dosing Information

Inclusion/Exclusion Criteria

Protocol Deviation

Neurological Examination

[figure not shown]
Ophthalmology Examination

Concomitant Procedures

16 INTERIM ANALYSES

No statistical interim analysis is planned.

17 FINAL SIGN-OFF FOR RIVUS PHARMACEUTICALS, INC, PROTOCOL RIV-HU6-203 STATISTICAL ANALYSIS PLAN

18 REVISIONS TO STATISTICAL ANALYSIS PLAN

Date	Revision
03 September 2021	The SAP was revised to analyze the HOMA-IR Calc only (i.e., the average of the 3 blood draws 5 minutes apart at each scheduled visit). Insulin, glucose, and C-peptide results will be listed only.
02 December 2021	Added summary statistics for placebo-corrected change-from-baseline values to each postbaseline time point for specified parameters and figures will be generated appropriate to the data output. Added responder status summary statistics for specified parameters at Day 61.
09 December 2021	For subjects in HbA1c 5.7% - 9.0% subgroup only, added summary statistics for change-from-baseline values to each postbaseline time point for specified parameters, placebo-corrected change-from-baseline values to each postbaseline time point for specified parameters, and MMRM or ANCOVA analysis as appropriate. Figures will be generated appropriate to the data output. In addition, added responder status summary statistics for specified parameters at Day 61. An addition, a criterion on body weight was added to the definition of Full Analysis Set (FAS).

16
